#### **Serious Adverse Events**

All SAEs occurring during the study must be reported to the appropriate sponsor contact person by study-site personnel immediately and within 24 hours of their knowledge of the event.

Information regarding SAEs will be transmitted to the sponsor using the SAE Form, which must be completed and signed by a physician from the study site, and transmitted to the sponsor within 24 hours. The initial and follow-up reports of a SAE should be made by facsimile (fax).

### **8.5.2. Method of Detecting Adverse Events and Serious Adverse Events**

Care will be taken not to introduce bias when detecting AEs or SAEs. Open-ended and nonleading verbal questioning of the participant is the preferred method to inquire about adverse event occurrence.

#### **Solicited Adverse Events**

Solicited AEs are predefined local (at the injection site) for which the participant is specifically questioned. Information on ISRs (Section 8.5.6.1) will be solicited.

#### **Unsolicited Adverse Events**

Unsolicited adverse events are all adverse events for which the participant is not specifically questioned.

### **8.5.3. Follow-up of Adverse Events and Serious Adverse Events**

Adverse events, including pregnancy, will be followed by the investigator as specified in Section 10.4, Appendix 4, Adverse Events: Definitions and Procedures for Recording, Evaluating, Follow-up, and Reporting.

### **8.5.4. Regulatory Reporting Requirements for Serious Adverse Events**

The sponsor assumes responsibility for appropriate reporting of adverse events to the regulatory authorities. The sponsor will also report to the investigator (and the head of the investigational institute where required) all suspected unexpected serious adverse reactions (SUSARs). The investigator (or sponsor where required) must report SUSARs to the appropriate Independent Ethics Committee/Institutional Review Board (IEC/IRB) that approved the protocol unless otherwise required and documented by the IEC/IRB.

### **8.5.5. Pregnancy**

All initial reports of pregnancy in female participants or partners of male participants must be reported to the sponsor by the study-site personnel within 24 hours of their knowledge of the event using the appropriate pregnancy notification form. Abnormal pregnancy outcomes (eg, spontaneous abortion, fetal death, stillbirth, congenital anomalies, ectopic pregnancy) are considered SAEs and must be reported using the SAE Form. Any participant who becomes pregnant during the study must discontinue further investigational intervention (JNJ-3989).

Follow-up information regarding the outcome of the pregnancy and any postnatal sequelae in the infant will be required.

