## 7. DISCONTINUATION OF INVESTIGATIONAL INTERVENTION AND PARTICIPANT DISCONTINUATION/WITHDRAWAL

### 7.1. Discontinuation of Study Intervention

With the implementation of Protocol Amendment 5, all participants had to stop JNJ-6379 treatment immediately.

Treatment with JNJ-3989 and/or PegIFN- $\alpha$ 2a must be discontinued if any of the criteria listed below apply. If JNJ-3989 is discontinued, PegIFN- $\alpha$ 2a should also be discontinued. If PegIFN- $\alpha$ 2a is discontinued, JNJ-3989 should be continued. NA treatment may be continued or, in consultation with the sponsor or discontinued based on investigator judgement.

- The participant withdraws consent to receive study intervention.
- The investigator believes that for safety reasons or tolerability reasons (eg, AE) it is in the best interest of the participant to discontinue JNJ-3989 (and, if applicable, PegIFN- $\alpha$ 2a).
- The participant becomes pregnant.
- The participant has a  $\geq$ grade 3 rash (see Section 10.5, Appendix 5, Rash Management) or allergic reaction (see Section 8.5.7.2).
- The participant has signs of hepatic decompensation (ie, clinical evidence of ascites, bleeding varices, or hepatic encephalopathy) or an increase in direct bilirubin  $>1.5$ x ULN in combination with INR  $\geq 1.5$ x ULN or albumin  $<3.0$  g/dL.
- The participant has a confirmed  $\geq$ grade 3 eGFRcr abnormality and a drop from baseline of  $>10$  mL/min/1.73 m^2, considered at least possibly related to JNJ-3989 (or PegIFN- $\alpha$ 2a) that persists despite changing tenofovir disoproxil to ETV or TAF (if the patient was receiving tenofovir disoproxil) (see Section 8.5.6.4).
- The participant has a confirmed QTcF prolongation (defined as a QTcF value of  $>500$  ms, or an increase from baseline of  $>60$  ms) at any given time point.
- The participant requires  $\geq 7$  days of treatment with any of the disallowed medications listed in Section 6.5 and does not intend to discontinue treatment with the disallowed medication.

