#### **8.5.6.4. Renal Complications**

If renal complications develop, participants should be closely monitored for disturbances in creatinine clearance. Additional investigations can be performed at the investigator's discretion. Participants must be treated as clinically appropriate.

Participants who develop confirmed grade 3 or 4 eGFRcr abnormalities with reduction from baseline by at least 10 mL/min/1.73 m^2 will change their NA from tenofovir disoproxil to ETV or TAF (if the patient was receiving tenofovir disoproxil), according to the prescribing information. If the abnormality persists despite change of NA or if the patient is not receiving tenofovir disoproxil, he or she will permanently discontinue the intake of JNJ-3989 (and PegIFN- $\alpha$ 2a, if applicable) if the abnormality is considered at least possibly related to JNJ-3989, and should be followed appropriately until resolution of AE or toxicity. Rechallenge is not allowed.

For all participants having received at least one dose of JNJ-6379, renal safety monitoring will be continued.

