**Table 6: Management of Rash Events by Severity Grade**

Definition	Study Intervention Action	Activities by Daya	Referral to Dermatologist and Dermatology Activities
Grade 3 rashb	
Vesiculation, moist desquamation, or ulceration OR
 
Any cutaneous event with 1 of the following:
 
 
- Elevations in AST/ALT <math>>2\times</math>baseline value
 
- Fever <math>>38^{\circ}\text{C}</math> or <math>100^{\circ}\text{F}</math>
 
- Eosinophils <math>>1.00\times 10^3/\mu\text{L}</math>
 
- Serum sickness-like reaction
 
	
Must permanently discontinue JNJ-3989; no rechallenge allowed
 
NA treatment may be discontinued based on investigator judgement in consultation with the sponsor
 
Day 0: required on-site visit.
 
Safety laboratory assessments required to be performed.
 
Digital pictures* of skin lesions may be taken at the investigator's discretion (recommended).
 
Determine if participant was adhering to the recommended sun-protective measures. If appropriate, provide sun protection counseling.
 
Day 1: required on-site visit.
 
Safety laboratory assessments required to be performed.
 
Digital pictures* of skin lesions may be taken at the investigator's discretion (recommended).
 
Further visit(s): appropriate follow-up required until resolution of rash or until clinical stability is reached.
 
Safety laboratory assessments and photography (digital pictures* of skin lesions) are recommended to be performed until the rash severity resolves to grade 2 or grade 1.
 
* Digital pictures to be taken at the clinical site upon consent of the participant.
	
Requiredc
 
Biopsy not required, but may be performed at the dermatologist's discretion.

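### Sections 8.5.5, 8.5.6.4 and Table 6 do not match the Section 7.1 stopping rules for PegIFN-α2a, and the gap matters once JNJ-3989 has been completed

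*Protocol*

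**What the plan says.** Protocol Section 7.1 states that JNJ-3989 and/or PegIFN-α2a "must be discontinued if any of the criteria listed below apply". Three items on that common list matter here:

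- **Pregnancy:** "The participant becomes pregnant".
- **Rash:** at least a "grade 3 rash (see Section 10.5, Appendix 5, Rash Management) or allergic reaction".
- **eGFR:** a confirmed abnormality of grade 3 or higher with a drop from baseline of more than 10 mL/min/1.73 m², "considered at least possibly related to JNJ-3989 (or PegIFN- $\alpha$ 2a) that persists despite changing tenofovir disoproxil to ETV or TAF".

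The same section links the two drugs: "If JNJ-3989 is discontinued, PegIFN- $\alpha$ 2a should also be discontinued". A second list in Section 7.1, for PegIFN-α2a only, mentions none of these three events.

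The event-specific text reads differently:

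- **Section 8.5.5 (pregnancy):** "Any participant who becomes pregnant during the study must discontinue further investigational intervention (JNJ-3989", closing the parenthesis after that one drug.
- **Table 6 in Appendix 5 (grade 3 and grade 4 rash):** "Must permanently discontinue JNJ-3989; no rechallenge allowed". NA treatment has its own line and PegIFN-α2a has none.
- **Section 8.5.6.4 (renal):** JNJ-3989 is stopped, and PegIFN-α2a where applicable, but only "if the abnormality is considered at least possibly related to JNJ-3989, and should be followed appropriately until resolution of AE or toxicity". The drop is given as at least 10 mL/min/1.73 m².

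The Description of Interventions table in Section 6.1 classes PegIFN-α2a as an investigational intervention.

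**The concern.** Optional PegIFN-α2a starts after the Week 40 biopsy and before the Week 48 visit, for 12 or 24 weeks. The last JNJ-3989 injection is at Week 44. Many PegIFN-α2a participants will therefore spend a large part of the course with no JNJ-3989 left to stop.

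In that period, a site that turns to the section for the event in hand finds no PegIFN-α2a action for pregnancy or for grade 3 or 4 rash. For an eGFR event attributed to PegIFN-α2a alone, it finds a rule that is not met, whereas Section 7.1 says it is met. At stake is consistent handling of mandatory safety stops for the only investigational drug still being given. Reporting is a lesser issue: SAP Section 5.2 tabulates treatment disposition, and SAP Section 1.2 counts PegIFN-α2a as a study treatment, so different readings would reach those tables.

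**Working it through.** **Step 1. Passages side by side.**

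| Event | Section 7.1 (JNJ-3989 and/or PegIFN-α2a) | Event-specific text | Relation |
|---|---|---|---|
| Pregnancy | Mandatory stop | 8.5.5: JNJ-3989 only | 8.5.5 is silent on PegIFN-α2a |
| Rash, grade 3–4 | Mandatory stop, refers to Appendix 5 | Table 6: JNJ-3989 only | Table 6 is silent on PegIFN-α2a |
| eGFR: action | Mandatory stop | 8.5.6.4: JNJ-3989, and PegIFN-α2a if applicable | Both drugs named |
| eGFR: causality | JNJ-3989 or PegIFN-α2a | 8.5.6.4: JNJ-3989 | Opposite answers if related to PegIFN-α2a alone |
| eGFR: drop (mL/min/1.73 m²) | More than 10 | 8.5.6.4: at least 10 | Differ at exactly 10 |

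Other event-specific sections do carry PegIFN-α2a alongside JNJ-3989: ALT/AST elevations (8.5.6.2), hematologic abnormalities (8.5.6.5), rash needing systemic corticosteroids (8.5.7.1) and allergic reactions (8.5.7.2). This suggests that its absence from 8.5.5 and Table 6 is an oversight.

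**Step 2. Does the linkage rule in 7.1 close the gap?** It is triggered by discontinuing JNJ-3989, so it works while JNJ-3989 is being given. After completion there is nothing to discontinue. The question is then how much of a PegIFN-α2a course falls in that period.

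**Step 3. Schedule arithmetic.** Inputs from the Schedule of Activities (1.3.1 and 1.3.3):

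- Week 40 biopsy on Day 281 ± 28 days, so the earliest is Day 253.
- Last JNJ-3989 injection on Day 309 (Week 44).
- Week 48 visit on Day 337, so the latest PegIFN-α2a start is about Day 336.
- Course length 12 × 7 = 84 days or 24 × 7 = 168 days.

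End day = start + length. Time past Week 48 = end − 337. Share after the last injection = (end − 309) / length, capped at 100%.

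| Start | Length | End day | Past Week 48 | Share after Day 309 |
|---|---|---|---|---|
| 253 (earliest) | 84 | 337 | 0 | 28/84 = 33% |
| 253 (earliest) | 168 | 421 | 84 d = 12 wk | 112/168 = 67% |
| 281 (nominal) | 84 | 365 | 28 d = 4 wk | 56/84 = 67% |
| 281 (nominal) | 168 | 449 | 112 d = 16 wk | 140/168 = 83% |
| 336 (latest) | 84 | 420 | 83 d ≈ 12 wk | 100% |
| 336 (latest) | 168 | 504 | 167 d ≈ 24 wk | 100% |

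Every full course outlasts the scheduled last injection. Section 6.4 allows a missed injection to be given up to 3 weeks late, on Day 330. Even then the earliest 12-week course, ending on Day 337, finishes after it.

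**The case against.** The strongest reply is that Section 7.1 already governs. It is the section on discontinuation, its lead-in is mandatory, it covers both drugs, and its rash item points to Appendix 5. Neither 8.5.5 nor Table 6 says to continue PegIFN-α2a, so a site can follow both texts at once. A reader might infer that these sections contradict 7.1. The documents do not support that: they are silent on PegIFN-α2a. This stands, and for pregnancy and rash the right word is incomplete. It does not dispose of the point, because the and/or in 7.1 does not say which drug each criterion stops, and the event-specific sections are where a reader would expect that answer.

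A reader might also infer that 8.5.6.4 omits PegIFN-α2a. It does not; its action names the drug. The mismatch there lies in the causality condition and the threshold. It gives opposite answers only for an event attributed to PegIFN-α2a alone, or for a drop of exactly 10.

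Other text narrows the gap. Besides the steroid-requiring rash and allergic-reaction rules, 7.1 lists serious acute hypersensitivity as an immediate PegIFN-α2a stop and allows discontinuation on the investigator's safety judgement. Pregnancy after JNJ-3989 has ended, and grade 3 or 4 rash outside these routes, remain without a matching event-specific instruction.

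Finally, counting from the Week 44 injection may be too strict. Section 6.6.1 treats JNJ-3989 as a fixed 48-week course, and SAP Section 5.1.3 counts 28 days after the last dose as on treatment. Measured from Week 48, the shortest overrun is zero. That is fair for the earliest 12-week course. Every 24-week course still runs at least about 12 weeks past Week 48.

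**Conclusion.** The point holds as an internal inconsistency. Sections 8.5.5 and Table 6 (grades 3 and 4) give no PegIFN-α2a action for events that 7.1 lists as mandatory stops. Section 8.5.6.4 applies a narrower causality condition and a slightly different threshold from 7.1. The exposed period is about 0 to 12 weeks past Week 48 for a 12-week course and about 12 to 24 weeks for a 24-week course. These figures assume full-length courses and starts anywhere from the earliest biopsy to just before Week 48. The minimum shares of 33% and 67% also assume the last injection is given on Day 309.

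Few participants are likely to be affected: the target is 24, PegIFN-α2a is optional, and highly effective contraception is required of women of childbearing potential. A reader might infer that discontinuation counts will be materially distorted. The documents give no rate from which to estimate that, and disposition is only summarised descriptively. The primary endpoint is untouched, because PegIFN-α2a starts after the Week 40 biopsy. The case for acting rests on patient safety and the small effort needed.

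**What to change.** Reconcile Section 7.1 with Section 8.5.5, Section 8.5.6.4 and the grade 3 and grade 4 rows of Table 6, so that:

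- each states the same action for PegIFN-α2a, explicitly including the period after JNJ-3989 has been completed;
- 7.1 makes clear, in place of the open and/or, which drug each of the three criteria applies to;
- 7.1 and 8.5.6.4 carry one causality condition and one eGFR threshold.

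Which action, condition and threshold apply is for the sponsor's clinical team to decide. The cost is a text clarification in these passages, with no change to sample size, data collection or analysis.

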### **8.5.6. Adverse Events of Special Interest**

Events of Special Interest are significant AEs that are judged to be of special interest because of clinical importance, known class effects or based on nonclinical signals. Events of Special Interest that will be carefully monitored during the study include ISRs, ALT/AST elevations, renal complications, hematological abnormalities, and events related to cholesterol increase (Section 8.4.4, Clinical Safety Laboratory Assessments). In addition, the following toxicities will also be carefully monitored: rash and acute systemic allergic reactions.

For participants reporting ALT/AST elevations, rash, ISRs, acute systemic allergic reactions, renal complications, and hematological abnormalities as specified in the DAIDS Toxicity Grading Scale (see Section 10.9, Appendix 9, DAIDS Table), the following should be done.

Note: renal complications and cholesterol increase are AESIs specific for JNJ-6379, which was part of the study intervention up to Protocol Amendment 4 and has been removed with the implementation of Protocol Amendment 5. Because participants who were enrolled before Protocol Amendment 5 was in effect, also received JNJ-6379 as part of their study intervention, the AESIs have not been revised with the removal of JNJ-6379. For all participants having received at least one dose of JNJ-6379, renal safety monitoring will be continued.

### 8.5.6.1. Injection Site Reactions

At the time points specified in the [Schedule of Activities](#) or at an unscheduled visit if needed, an evaluation of the injection site will be performed based on participant's description and/or physical examination. Evaluations will be recorded in the source documents and will include at a minimum the time of occurrence, time of resolution and a description of the abnormality including its maximal diameter. For each ISR, information on pain, erythema, induration and pruritus should be obtained as specified in the DAIDS scale (see Section [10.9](#), Appendix 9, DAIDS Table).

All ISRs (including ISRs below grade 1) should be recorded in the special events section of the CRF.

Digital pictures will be taken when considered appropriate; all efforts should be made to collect images in case of grade 3 and 4 ISRs. Digital pictures will only be taken and collected from participants who consent separately to this component of the study. If digital pictures are required, they should be de-identified and provided to the sponsor.

### 8.5.6.2. Intervention-emergent ALT/AST Elevations

Elevated liver enzyme activity can be triggered by the underlying HBV disease as well as by the study intervention.

Management of intervention-emergent ALT/AST elevations is presented graphically in Section [10.6](#), Appendix 6, Intervention-emergent ALT/AST Elevations, and is described below.

Any intervention-emergent elevation of ALT and/or AST  $\geq 3$ x ULN and  $\geq 3$ x nadir (ie, lowest value during study participation) should trigger an assessment of confounding factors (alcohol intake, change in concomitant medication, and comorbidities) and should trigger a confirmatory study visit to repeat laboratory testing of ALT, AST, ALP, AFP, bilirubin (total and direct), INR, albumin, and HBV DNA. Additional tests should be considered based on clinical judgement (refer to Section [10.6](#), Appendix 6, Intervention-emergent ALT/AST Elevations). The confirmatory visit should be scheduled as soon as possible, preferably within 7 days of the receipt of the initial ALT/AST results. In case the repeat laboratory testing shows an isolated ALT/AST elevation (ie, with stable albumin, bilirubin [total and direct], and INR) the participant may continue study intervention. In case of confirmed ALT elevation  $>1,000$  U/L and  $\geq 3$ x the baseline value, JNJ-3989 (and PegIFN- $\alpha$ 2a, if applicable) should be discontinued. In both cases, NA treatment should be continued. The participant will be monitored on a weekly basis (laboratory testing of ALT, AST, ALP, AFP, bilirubin [total and direct], INR, albumin, and HBV DNA) until ALT and AST levels have returned to  $<5$ x ULN and HBV DNA is  $<20,000$  IU/mL.

If the ALT and/or AST level is  $\geq 3$ x ULN and  $\geq 3$ x nadir and is associated with any of the following laboratory results or clinical symptoms:

- INR  $\geq 1.5$ , OR
- direct bilirubin  $>1.5$ x ULN, OR
- serum albumin  $<3.0$  g/dL, OR

- ascites, hepatic encephalopathy, or liver-related symptoms (eg, severe fatigue, nausea, vomiting, right upper quadrant pain in the absence of an alternative medical explanation), OR
- other indication of reduced liver function

the participant should discontinue JNJ-3989 (and PegIFN- $\alpha$ 2a, if applicable) and should be monitored on a weekly basis or as per good clinical practice until ALT and AST levels have returned to  $<5$  x ULN and HBV DNA is  $<20,000$  IU/mL and, if present, liver-related symptoms have improved. NA treatment should be continued. Additional tests should be considered based on clinical judgement (refer to Section 10.6, Appendix 6, Intervention-emergent ALT/AST Elevations).

In case of prolonged ALT elevation  $>3$  x ULN AND  $>2$  x nadir, which lasts at least 12 weeks, the decision to continue JNJ-3989 and/or PegIFN- $\alpha$ 2a should be based upon virologic parameters (eg, HBsAg, HBV DNA) and should be made in consultation with the sponsor.

PegIFN- $\alpha$ 2a may need to be discontinued in clinically significant cases of ALT increase or in combined increase of ALT and direct bilirubin. Refer to the prescribing information for PegIFN- $\alpha$ 2a.

The NA re-treatment criteria during follow-up are presented in Section 6.6.2.

#### **8.5.6.3. Complications From Liver Biopsy**

Participants should be closely monitored for liver biopsy complications. Infection and internal bleeding and/or puncture of other internal organs (gall bladder, lung, intestine or kidney) can lead to serious complications (uncommon 1 in 1000 to 1 in 100) including the need for emergency surgery, blood transfusion or removal of organs. Deaths directly related to liver biopsy occur rarely (approximately 1 in every 10,000 biopsies). Criteria for participant selection and laboratory assessments are in place to minimize these risks. Additional investigations can be performed at the investigator's discretion. Participants must be treated as clinically appropriate.

#### **8.5.6.4. Renal Complications**

If renal complications develop, participants should be closely monitored for disturbances in creatinine clearance. Additional investigations can be performed at the investigator's discretion. Participants must be treated as clinically appropriate.

Participants who develop confirmed grade 3 or 4 eGFRcr abnormalities with reduction from baseline by at least 10 mL/min/1.73 m^2 will change their NA from tenofovir disoproxil to ETV or TAF (if the patient was receiving tenofovir disoproxil), according to the prescribing information. If the abnormality persists despite change of NA or if the patient is not receiving tenofovir disoproxil, he or she will permanently discontinue the intake of JNJ-3989 (and PegIFN- $\alpha$ 2a, if applicable) if the abnormality is considered at least possibly related to JNJ-3989, and should be followed appropriately until resolution of AE or toxicity. Rechallenge is not allowed.

For all participants having received at least one dose of JNJ-6379, renal safety monitoring will be continued.

### **8.5.6.5. Hematologic Abnormalities**

Mild thrombocytopenia was observed in recently conducted non-clinical toxicology studies with the combination of JNJ-3989 and JNJ-6379. In addition, in a 3-month combination study with 80 rats, 1 rat developed pancytopenia related to bone marrow depletion after 23 days of dosing. Previously, in a 9-month dog study in 24 dogs treated with JNJ-6379 alone, pancytopenia which correlated with a marked increase in plasma cell-like cells in the bone marrow was observed in 1 dog after 60 days of dosing.

No thrombocytopenia or pancytopenia has been observed in the ongoing JADE study (56136379HPB2001) investigating JNJ-6379/Placebo with or without NA treatment. All 232 participants have completed at least 24 weeks of study intervention. In a Phase 1 study with JNJ-3989, mild (Grade 1) transient thrombocytopenia was observed in 6 out of 84 participants receiving 3 SC injections of JNJ-3989 alone over a period of up to 12 weeks with background of NA. The transient thrombocytopenia was not considered clinically significant. No thrombocytopenia or pancytopenia was observed in 12 participants when JNJ-3989 and JNJ-6379 were given in combination over a 12-week period.

Based on the non-clinical findings, any relevant abnormalities in hematologic parameters will be carefully monitored as described below:

- Platelet counts: <100, 000 cells/mm^3 (at least Grade 2 [DAIDS]) or <100 GI/L or reduction from baseline by at least 50% baseline
- Hemoglobin: Decrease from baseline of at least 2 g/dL from baseline or at least Grade 2 (DAIDS)
- Reticulocyte count: Reduction to <0.5% of the RBC count
- Neutrophil count: Treatment-emergent reduction to at least Grade 2 (DAIDS)

In case any one of the above criteria are met, a confirmatory visit should be scheduled as soon as possible, preferably within 7 days of the receipt of the initial results. Confirmation of the results will trigger weekly or biweekly (every other week) unscheduled visits until improvement or stabilization of the respective parameter(s). Stabilization is defined as no further significant reduction over two consecutive visits.

In case of confirmed Grade 3 or Grade 4 hematologic abnormalities, discontinuation of JNJ-3989 (and PegIFN- $\alpha$ 2a, if applicable) should be considered. In case of discontinuation, NA treatment should be continued.

